Primary measure: Computerized Tower of London (cTOL) total time, time to first move and optimal moves). We have found significant improvement in cTOL following GMT in previous cohorts of Veterans with blast-related mTBI and anticipate improvement following a combined intervention.

Secondary measure: Attention Network Task (ANT) reaction time and errors for one or all dissociable components of three attentional systems (orienting, alerting, executive control) following intervention. There is little understanding of components of impaired attention and how it impacts executive function; therefore, there is limited guidance in shaping cognitive training. We will conduct an experimental task (attention network task) that disassociates three attentional components (alerting, orienting, and executive control). We will specifically target the orienting component of attention that is problematic for Veterans with mTBI and PTSD^{24, 26}. Attentional processes are vital to goal-directed behavior. There is great potential in the use of these measures to identify individual differences (type of attention deficit) that could moderate treatment-related improvement and inform targeted interventions.

Hypothesis 2: Treatment gains will translate to functional activities compared to controls.

Primary measure of functional performance: test of grocery shopping skills (TOGSS) total time and optimal strategy use. The TOGSS captures efficiency in completing a real-world task and aligns with the strategy skills learned in GMT.

Secondary measure of community participation, the Community Reintegration of Servicemembers (CRIS) extent of participation. The CRIS demonstrated significant GMT treatment effect compared to controls in Veterans with mTBI. The combined treatment of attention training using drill training and implementing strategies to improve attention in a functional setting through GMT will potentiate treatment effect to functional activities. Measuring functional improvement through performance-based measures and self-report of engagement in activities will demonstrate treatment translation.

Tertiary analysis will be conducted on moderator variables: PTSD symptoms, Pain, History of Substance Abuse, Depression, number of concussions and combat exposure.

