Randomization Procedure: 25 of the Veterans will be randomized to treatment while 25 will engage in BHW/movies as control participants. The Pocock-Simon covariate adaptive randomization procedure will be used so that, for each PTSD severity category, approximately 50% (25/25) of Veterans are assigned to treatment group; consequently, there will be approximately equal proportion of PTSD participants assigned to the treatment and control groups.

Each group of the 25 treatment and 25 control participants will also be randomized to training to complete the Test of Grocery Shopping skills in a virtual setting (V-Mart) during session 7 or 8.

Intervention

GMT: is a 10-session intervention to improve planning and problem solving. Interactive Power Point modules are administered by a cognitive therapist. Each session builds on the steps of a five-stage planning and problem-solving strategy. Veterans will be taught to generate and verbalize the following five-steps: "stop-what am I doing?", "define the goal", "list the steps", "learn the steps"; then, "check-am I doing what I planned?" The five-stage strategy is then incorporated into a variety of activities in the laboratory and in-home assignments. At each session, the participant discusses utilization of the strategies in daily life and reviews progress. The following steps are taught during simulated tasks: 1) Identify Main Goal; 2) Break down task into sub-goals and steps for each goal; 3) List supplies needed; 4) Recognize potential barriers to completing goal; 5) Determine strategy to accomplish task; 6) Prepare to begin task with "presence of mind" exercise; 7) State goal out loud; 8) Begin task and stop self frequently to state main goal out loud and check to be sure one is working toward the goal (on target).

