Test of Grocery Shopping Skills (TOGSS): is a performance-based measure of a person's ability to locate items in an actual grocery store. In addition to measuring specific grocery shopping skills, TOGSS scores are associated with cognitive abilities, particularly executive functioning (Rempfer, Hamera, Brown, & Cromwell, 2003; Zayat, 2006). TOGSS administration is 20-30 minutes. The examinee is shown a grocery list of 10 specific items and asked to locate the lowest priced brand for each one. Outcome variables (accuracy, speed and efficiency) will be tested to determine improvement in functional performance (HO#2). Veterans will have the option of practicing shopping in a virtual grocery store displayed on a monitor using a game controller to navigate prior to completing the TOGSS in an actual grocery store. Both the Veteran and the clinician will identify barriers to efficient shopping and will plan strategies to overcome barriers.

3. Secondary Measures:

Attention Network Task (ANT): presents participants with a target item (>) on a computer screen surrounded by congruent (> > > > >), neutral (- - > - -), or incongruent flanker stimuli. Stimulus presentation is preceded by different cue conditions and the participant is instructed to identify the target stimulus and respond by selecting 1 or 5 on the computer keyboard. To characterize the type of attention deficits of each participant, we will use the attention network task (ANT) to determine the relationship with the alerting, orienting and executive aspects of attention to treatment effects. Given the success of the ANT in discriminating impairment among the three attentional networks in Veterans with mTBI and PTSD, we will utilize this method to study differential response of attention networks to cognitive remediation (Ho #1, secondary measure).

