For both Hypothesis 1 and 2: A multiple linear regression model will be used to determine if there is a significant difference between the treatment and control groups in tests of cognition and function. Separate models will be fit for each outcome measure (cTOL, ANT, TOGSS, CRIS) the baseline measure and treatment group indicator will be used as covariates in the model. The Wald test will be used to determine if the coefficient for treatment group is significantly different from zero, indicating a significant treatment effect. Effect sizes for between-group differences will be estimated using the coefficient of the group indicator in the model.

Tertiary analysis: Other moderator variables (Table 2) will be examined to determine whether a linear relationship exists between changes in problem solving, attention or participation. These variables include PCL-5 total score and index scores (such as intrusions), BPI total score, AUDIT-C total score, BDI-II total score, number of concussions, STAXI-2, PSQI, MFIS and CES total score.

Sample Size: A sample size of 50 participants equally randomized into treatment or control groups will yield 80% power to detect an effect size of 0.81³⁹. In other words, if the true improvement in the treatment group is 0.81 standard deviations greater than the control group, then the pilot study has an 80% chance of detecting a significant difference. Based on our preliminary analysis of 14 GMT and 3 BHW controls, we estimate a large effect size of 1.76 (3.16, 0.37) for the cTOL time to first move, a moderate effect size of 0.827 (-0.46, 2.10) for cTOL optimal moves, and a moderate effect size of 0.67 (-0.60, 1.95) for cTOL time to completion⁴⁰.

7. Possible Discomforts and Risks:

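### As written, control Veterans can be coached in two of the GMT task steps on the grocery task that is scored as the Hypothesis 2 primary outcome, which may dilute the TOGSS contrast.

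*Combined protocol and SAP*

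**What the plan says.** All references are to the combined protocol and SAP.

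- **Outcome.** Under Specific Aims, Hypothesis 2, the primary measure is "test of grocery shopping skills (TOGSS) total time and optimal strategy use". The reason given for choosing it is that "The TOGSS captures efficiency in completing a real-world task and aligns with the strategy skills learned in GMT". Table 2 schedules it at weeks 1, 11 and 36.
- **Who is trained for it.** Under Randomization Procedure: "Each group of the 25 treatment and 25 control participants will also be randomized to training to complete the Test of Grocery Shopping skills". The setting is V-Mart, at session 7 or 8. Table 2 lists V-Mart at 20 minutes.
- **What accompanies the practice.** The TOGSS entry in Description of Measures makes virtual practice an option for Veterans, without naming an arm, and continues: "Both the Veteran and the clinician will identify barriers to efficient shopping and will plan strategies to overcome barriers".
- **GMT content.** The Intervention section lists eight steps taught in simulated tasks, among them "4) Recognize potential barriers to completing goal; 5) Determine strategy to accomplish task".
- **Control content.** The Control Group section describes the Brain Health Workshop with readings and quizzes, and geographic movies with a short quiz. It lists no strategy training.
- **Analysis.** In the Statistical Analysis Plan, "the baseline measure and treatment group indicator will be used as covariates in the model". The model has no term for V-Mart or for coaching.

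**The concern.** Hypothesis 2 asks whether what is learned in treatment carries over to everyday activity better than in controls. The comparison needs controls who have not been taught the strategies under test, at least not on the task that is scored. Read together, the passages allow a clinician to sit with a control Veteran before the week 11 TOGSS, work out what hinders efficient shopping and plan how to deal with it. That is part of the experimental content, applied to the outcome task.

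Treated Veterans will by then have met these steps in GMT, so the same session may add less for them than for controls. If so, the difference between arms shrinks on a primary outcome in a trial of 25 per arm, where there is little power to spare. The planned model would not correct this. The baseline TOGSS is taken before V-Mart, and a gain that differs by arm is an interaction, which could only be explored at this sample size.

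**Working it through.** **1. Does the text allow it?** Three passages bear on this.

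- Randomization Procedure: controls are named among those assigned to V-Mart training.
- TOGSS description: barrier and strategy planning goes with the shopping practice, and no arm is named.
- Control Group: only education, movies and quizzes are listed.

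The first two permit coaching of controls. The third does not provide for it, but does not forbid it. Session 7 or 8 falls within the 10-session intervention, so any coaching precedes the week 11 and week 36 TOGSS.

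**2. How much of GMT is involved?** Identifying barriers corresponds to step 4 and planning strategies to step 5. That is two of eight steps, around one 20-minute V-Mart exercise.

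**3. The plan's own power figure.** Inputs from the Sample Size paragraph and Randomization Procedure are 25 per arm and an effect of 0.81 SD. Alpha is not stated; I assume two-sided 0.05, since "The Wald test will be used to determine if the coefficient for treatment group is significantly different from zero" describes a two-sided test. For a two-sample t-test the non-centrality is 0.81 × √(25/2) = 2.86 on 48 degrees of freedom, and power is 80.1%. The stated 80% is reproduced. A one-sided test would give 88.1%, which does not match.

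**4. Effect of coaching on the contrast.** Let *q* be the share coached in each arm, *c* the gain of a coached control, and *t* the extra gain of a coached treated Veteran, both gains as fractions of 0.81 SD. Then

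contrast = 0.81 × [1 − q(c − t)].

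Only the difference c − t matters. The documents give none of *q*, *c* or *t*, and 0.81 is the detectable effect of the design, not an estimate for the TOGSS (the preliminary estimates are for the cTOL only). All the values below are assumptions.

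| q | c | t | Contrast (SD) | Power |
|---|---|---|---|---|
| any | equal to t | equal to c | 0.81 | 80% |
| 0.25 | 0.25 | 0 | 0.81 × 0.9375 = 0.76 | 75% |
| 0.5 | 0.25 | 0 | 0.81 × 0.875 = 0.71 | 69% |
| 0.5 | 0.5 | 0.25 | 0.81 × 0.875 = 0.71 | 69% |
| 0.5 | 0.5 | 0 | 0.81 × 0.75 = 0.61 | 56% |
| 1 | 0.25 | 0 | 0.81 × 0.75 = 0.61 | 56% |

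The last row covers the reading in which every participant is trained and only the session (7 or 8) is randomised. At 0.61 SD, 44 per arm would be needed for 80% power.

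**The case against.** The strongest reply is that both arms receive the same session. If it adds the same amount in each, the first row of the table applies and nothing is lost. This stands: the harm depends on controls gaining more than treated Veterans, which is plausible but not shown in the documents.

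Second, the planning sentence sits in a description of a measure and mirrors GMT. The sponsor may intend it for the treatment arm only, as the Control Group section would suggest. A reader might infer that controls will certainly be coached, but the text does not establish that. It only fails to rule it out, and a therapist following it could coach a control.

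Third, one short exercise covering two of eight steps is small beside ten GMT sessions and home attention training five days a week. The documents do not support treating it as GMT delivered to controls, or expecting it to yield a large part of the treatment benefit. This stands and favours the smaller losses in the table.

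A reader might also infer that a positive TOGSS result would show only rehearsal of the task. That does not follow if practice is balanced between arms, because the hypothesis is comparative and shared practice cannot by itself produce a difference. It would become a problem if coaching or uptake differed by arm, which the optional wording leaves open.

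**Conclusion.** The concern holds in a conditional form. The plan permits part of the GMT strategy content to reach controls on the task scored as the Hypothesis 2 primary outcome, and neither the control description nor the model deals with it. Dilution is likely if controls gain more than treated Veterans, and absent if both gain equally. With half of controls coached, no extra gain in coached treated Veterans and two-sided alpha 0.05, control gains of 25% or 50% of the effect reduce 0.81 SD to 0.71 or 0.61 SD, and power from 80% to 69% or 56%. These figures show sensitivity and are not predictions. The sample-size calculation itself is sound. The point deserves correction because it touches a primary outcome and is cheap to remove.

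**What to change.** 1. In Randomization Procedure and in the TOGSS description, limit the V-Mart step to navigation practice with the controller, in both arms.
2. Delete the clinician-led identification of barriers and planning of strategies for the shopping task before the week 11 TOGSS.
3. Reconcile the two passages on V-Mart: one randomises it, the other makes it optional. If it is randomised, say whether the allocation is to training or no training, or only to session 7 or 8.

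The planning should not be withheld from controls alone. Treated Veterans would then be rehearsed on the scored task and controls not, and a positive result could reflect that practice. Nor does this point call for restricting Goal Attainment Scale goals or homework, which are individualised therapy content.

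The cost is protocol wording and an instruction to therapists, with no new visit or procedure. The downside is that treated Veterans lose a short planning exercise specific to shopping.

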Successful completion of the proposed study will provide insight into the effectiveness of the innovative combined treatment of attention and executive function in Veterans with mTBI and PTSD. Use of the ANT could better target treatment and lead to future examination of attention treatment on neuroplasticity.

6. Research Plan:

This is a pilot study to test the effect of GMT plus Attention Training for Veterans with chronic mTBI. The research design is a parallel study with randomization to treatment or control with test administration at pre/post and six months following treatment.

Patients for the treatment and control group: participants that meet the inclusion criteria and exclusion criteria will be scheduled for a session to consent and begin screening tests to determine inclusion criteria #4 and exclusion criteria #4 and #5.

We will recruit 50 Veterans for the study (25 treatment; 25 control) and 50 informants:

1. all Veterans who have served in OIF-OEF-OND (Operation Iraqi Freedom-Operation Enduring Freedom-Operation New Dawn) with single- (at least brief loss of conscious) or multiple (with at least alteration of consciousness) mild traumatic brain injury (mTBI) during deployment, who seek services at North Florida/South Georgia Veterans Health System (NF-VHS).
2. TBI must have suffered their injury at least 6 months prior to study enrollment and currently be in stable neurological condition.
3. age range 18-55 years to reduce the impact of aging on treatment improvement.
4. Attention deficit of ≥ 1.5 SD below the mean of the Repeatable Battery for the Assessment of Neuropsychological Status attention index. This will ensure that participants have an objective attention deficit.
5. Family member or friend that is willing to complete the BRIEF-A (BRIEF-A guidelines of face-to-face interaction with the participant at least twice a week) at all measurement timepoints.
6. Access to a home computer, or smartphone with internet access.

Classification of Mild TBI severity will be determined from the Ohio State University TBI Identification Short-Form, and the updated 2015 VA/DoD classification detailed below in Table 1 for the mild criteria:

Criteria	Mild	Moderate	Severe
Structural imaging	Normal	Normal or abnormal	Normal or abnormal
Loss of Consciousness (LOC)	0-30 min	>30 min and <24 hours	>24 hours
Alteration of consciousness/ mental state (AOC)	up to 24 hours	>24 hours; severity based on other criteria	

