Control Group: Participants that are randomized to this group will provide a control for repeat testing and will provide similar characteristics with the treatment group, such as severity of PTSD. To equate for time and exposure to therapist, the participants will engage in a Brain Health Workshop (BHW) and watch geographic movies. BHW was developed specifically for consistency with GMT session length and contact with the facilitator⁴⁹. BHW is an education presentation on brain function and cognitive principles of learning with homework (readings assigned) and quizzes on information covered. To match time and contact of attention training, control participants will meet with the therapist for a separate two-hour session from BHW and watch geographic movies followed by a short quiz. This will equate the amount of time and contact experienced by the treatment group for both the GMT and attention training sessions.

Measurement: Veterans with mTBI will qualify for the study if they demonstrate a deficit in attention as measured by formal neuropsychological testing and pass effort testing. The following measures (Table 2) will be administered at week 1 (before intervention), week 11 (after intervention) and at week 36 (six months after intervention). The primary outcome measures for Aim 1, will be the computerized Tower of London (cTOL)³⁸ and the Test of Grocery Shopping Skills (TOGGS).

The following measures will be administered by an email link from the University of Florida REDCap application: Combat Exposure Scale, Neurobehavioral Symptom Inventory, Beck Depression Inventory, Alcoholic Use Disorders Identification Test, PTSD Checklist for DSM5, Brief Pain Inventory, Behavioral Rating Inventory of Executive Function for Adults, and State Trait Anger Expression Inventory.

Table 2. Study Measures			
Domain	Purpose	Administration session	Measure(s)/Minutes to Administer
Pre-Treatment Screening/Assessment			
Attention	Attention impairment	Weeks	RBANSAttention index
Effort	Determination of potential suboptimal effort	1	*TOMM/5
Word-reading	For group matching—estimation of pre-morbid cognitive ability	1	*NAART/10
Primary Outcome Measures			
Executive Function	Assesses problem-solving, planning and attention	1, 11, 36	cTOL/20
Functional	Assess performance of a complex task	1, 11, 36 7 or 8	ToGSS./30 V-Mart/20
Secondary Outcome Measures – Cognition			

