Tower of London (TOL): is a computerized program in which patients are shown two pictures simultaneously of a goal board and a test board (Unterrainer et al, 2006). Each picture shows three balls of different colors arranged on three pegs, with the balls in a unique arrangement in each picture. Patients are instructed to determine the fewest possible moves of the balls in the test picture to make the arrangement of balls identical to that of the goal picture within 60 seconds. The screen reports whether the response is correct or incorrect. Test administration is less than 30 minutes for each session (pre/post/follow-up). Each set consists of 30 problems of variable difficulty, determined by variables, such as, the number of moves needed to solve the problem (Berg and Byrd, 2002). In turn, each set consists of the same number of 4, 5, 6 or 7 move problems and has the same average difficulty level. Difficulty rating is based on global and specific problem parameters shown to affect the planning process (Kaller, 2007, 2008, 2009; Berg, Byrd, McNamara, & Case, 2010; Kaller, Unterrainer, Rahm, & Halsband, 2004). The dependent variables are the total time spent solving the problem and the optimal moves made toward the goal display. Based on our previous studies, executive function represents three factors (behavior regulation, emotional regulation and metacognition) (Waid, Wen, Heaton, and Velozo, submitted to Neuropsychology). GMT is a metacognitive training with emphasis on planning prior to engaging in a complex task. Therefore, a primary measure that captures the planning and problem solving of a multi-step task, called the Tower of

London (TOL), was selected. Based on results from our preliminary study, the dependent variables of total time and optimal moves will be used to determine treatment effect. While not all of the participants in our previous work demonstrated significant improvement on these variables, group differences based on paired T-tests were significant in Total Time ($p=0.026$) and Optimal Moves ($p=0.022$) from baseline to treatment. In addition to our findings, Levine (2011) demonstrated a significant change in the TOL following GMT for a mixed neurological sample compared to a control group. Thus, the TOL appears to be sensitive to the effects of GMT and will be compared from post and 6-month follow-up to screening to determine treatment gains (HO#1).

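### The planned regression names no visit and has no missing-data rule, so the six-month comparison would by default lose Veterans seen only at week 11; a repeated-measures model per outcome would keep them

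*Combined protocol and SAP*

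**What the plan says.** The Measurement part of section 6 schedules the outcome measures before treatment, at "week 11 (after intervention) and at week 36 (six months after intervention"). The Tower of London entry under Primary Treatment Outcome Measures says the test "will be compared from post and 6-month follow-up to screening to determine treatment gains (HO#1"). A six-month result is therefore intended for at least one primary outcome.

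For both hypotheses the Statistical Analysis Plan states: "A multiple linear regression model will be used to determine if there is a significant difference between the treatment and control groups". It continues: "Separate models will be fit for each outcome measure (cTOL, ANT, TOGSS, CRIS"), with the baseline value and the group indicator as the only covariates. Inference is by "The Wald test will be used to determine if the coefficient for treatment group is significantly different from zero".

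The plan does not say which visit supplies the dependent variable. It has no visit or group-by-visit term and no within-person correlation, and it gives no analysis set, missing-data rule or dropout allowance. The Sample Size paragraph rests on "A sample size of 50 participants equally randomized into treatment or control groups" and does not name the visit to which its effect size applies.

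**The concern.** A linear regression on baseline and group takes one follow-up value per Veteran. To deliver comparisons at weeks 11 and 36 it has to be fitted once per visit, and ordinary software drops anyone whose value at that visit is missing. A Veteran with a week-11 score but no week-36 score then contributes nothing to the six-month comparison, although the week-11 score carries information about the missing one.

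Two things are at stake, both at week 36. Precision is lost in a trial with 25 per arm. If those who leave differ between arms in how they were doing at week 11, the six-month estimate can also be biased.

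**Working it through.** **Inputs from the documents.** The recruitment plan is "We will recruit 50 Veterans for the study (25 treatment; 25 control) and 50 informants". The target is 80% power for an effect of 0.81 SD, described as "if the true improvement in the treatment group is 0.81 standard deviations greater than the control group".

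**Assumptions, because the documents are silent.** Two-sided alpha is 0.05. Everyone is seen at week 11, and 10%, 20% or 30% are lost by week 36. The correlation of baseline with each follow-up is 0.5. The week 11-36 correlation is 0.7, with 0.5 and 0.85 as a range.

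**Step 1: the plan's own figure.** A two-sample t-test with 25 per arm and d = 0.81 has 80.1% power (noncentral t). The stated 80% reproduces, provided all 50 Veterans have the analysed value.

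**Step 2: correlation after baseline adjustment.** r = (0.7 - 0.5 x 0.5) / (1 - 0.5 x 0.5) = 0.45 / 0.75 = 0.6. The residual SD is sqrt(0.75) = 0.866.

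**Step 3: precision under random loss.** Let d be the fraction lost and m = 25(1 - d) the completers per arm. In residual-variance units, the per-arm variance at week 36 is 1/m for complete-case regression and (1 - r^2)/m + r^2/25 for the repeated-measures estimate. Their ratio is 1/(1 - r^2 d). At 20% loss: 1/20 = 0.0500 against 0.64/20 + 0.36/25 = 0.0464, a ratio of 1.078 and an effective 21.6 per arm instead of 20.

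**Step 4: bias under selective loss.** Suppose controls leave at random, and treated Veterans leave only if they scored below the value expected from their baseline and arm. That half lies on average 0.798 residual SD below expectation. The treated Veterans who remain therefore average 0.798 d/(1 - d) residual SD above it at week 11. The part carried to week 36 is 0.6 x 0.866 times this. At 20% loss: 0.798 x 0.2/0.8 = 0.1995, and 0.1995 x 0.6 x 0.866 = 0.104 SD.

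| Loss by week 36 | Variance ratio | Bias, treatment arm only | Power, complete-case | Power, repeated measures |
|---|---|---|---|---|
| 10% | 1.04 | +0.05 SD | 75.7% | 77.3% |
| 20% | 1.08 | +0.10 SD | 70.4% | 73.8% |
| 30% | 1.12 | +0.18 SD | 64.3% | 69.5% |

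The power columns assume random loss and use the scale on which Step 1 reproduces 80%, with no credit for baseline adjustment.

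**Step 5: simulation of the same setting.** Complete-case bias was about +0.045, +0.105 and +0.18 SD at the three loss rates, against near zero for the likelihood estimate. Variance under random loss was about 4%, 8% and 14% higher; the 14% is slightly above the formula because the number lost varies from trial to trial. With 20% selective loss and no true effect, the complete-case false-positive rate was about 7%, against 5% for the likelihood estimate. When the same poor-performer loss was applied to both arms, complete-case bias was essentially zero.

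**Step 6: range over the correlation, at 20% loss.** For a week 11-36 correlation of 0.5, r = 0.25/0.75 = 0.33, giving a variance ratio of 1.02 and a selective-loss bias of 0.06 SD. For 0.85, r = 0.60/0.75 = 0.8, giving 1.15 and 0.14 SD.

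**Step 7: a different selective mechanism.** Suppose loss in the treated arm rises smoothly as the week-11 score worsens, with about 27% of that arm and 20% of controls lost and an adjusted correlation of 0.7. The complete-case estimate then moves from 0.81 to about 1.02 residual SD, with a false-positive rate of about 10%. The size of the bias depends on the mechanism as well as on the amount of loss.

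**The case against.** **The regression itself is not at fault.** The same baseline-and-group regression, with week-36 values multiply imputed from week 11, would use essentially the same information under the same assumption. This stands: the weakness is the model together with the absence of any missing-data rule. A repeated-measures model is the simpler remedy because it also forces the visit to be named.

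**The plan does not prescribe single-visit fits or discarding.** A reader might take the word separate in the quoted sentence to mean one model per visit. It means one model per outcome. Visit-by-visit fitting and the loss of incomplete cases are the default consequences of the model's form, not stated intentions.

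**Bias is conditional.** A reader might infer that the six-month benefit will be overstated. The documents do not support that. Bias needs loss that is related to week-11 performance and differs by arm. Home burden does differ: daily BrainHQ practice in one arm, readings and quizzes in the other. Against that, therapist time is matched and Veterans are reimbursed for each session. No attrition figure is given. At 20% loss the bias of 0.10 SD compares with a standard error of about 0.866 x sqrt(2/20) = 0.27 SD.

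**The gain is modest and falls on week 36.** If loss occurs after week 11, the week-11 contrast is essentially the ordinary baseline-adjusted regression. With complete data the two methods agree at week 36 as well, so leaving out the within-person correlation does no harm in itself.

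**Conclusion.** The concern holds in limited form. The plan intends comparisons at both follow-ups but names no visit in the model, gives no analysis for week 36 and has no rule for missing values. By default the six-month comparison loses Veterans who have informative week-11 data.

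Under the stated assumptions the cost at week 36 is about 4-14% more variance than necessary with random loss. That corresponds to roughly 2 to 5 points of power at 10-30% loss (77.3 - 75.7 = 1.6; 69.5 - 64.3 = 5.2). An overstatement of about 0.05-0.18 SD arises only if poor week-11 performers leave the treatment arm selectively. All of this rests on assumed loss rates and correlations.

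It would also be too strong to say that a repeated-measures model uses all data or secures the six-month result. Veterans with neither follow-up add essentially nothing to the contrast, full power is not restored, and the bias is removed only if missingness depends on observed data. The change is still worth making, because it is cheap and settles which visit is primary.

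**What to change.** In the Statistical Analysis Plan, replace the regression paragraph with one mixed model for repeated measures per outcome variable:

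- **Population:** all randomised Veterans with at least one follow-up value, analysed as allocated.
- **Terms:** group, visit (11, 36), group-by-visit, baseline and baseline-by-visit.
- **Covariance and inference:** unstructured covariance, with Kenward-Roger degrees of freedom.
- **Contrasts:** name the week-11 group contrast as primary and the week-36 contrast, from the same model, as the test of durability.
- **Missing data:** state that validity assumes missingness depends on observed data. Add a simple sensitivity analysis for data missing not at random, for example shifting imputed week-36 values in the treatment arm by increasing amounts until the conclusion changes.

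The cost is one paragraph and a little more programming. With two follow-up visits the unstructured covariance needs three parameters and the fixed part six (intercept, group, visit, group-by-visit, baseline, baseline-by-visit), which is feasible with 50 Veterans. No extra data or participants are needed.
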